1. STUDY TITLE

A Multicenter, Open Label, A Phase 4, Double-Blind, Randomized, Placebo-Controlled, Multicenter Study Evaluating the Effect of Obeticholic Acid on Clinical Outcomes in Subjects with Primary Biliary Cholangitis

The COBALT Study: Clinical Outcomes with Obeticholic Acid in Liver Treatment (COBALT)
Study Protocol Number: 747-302

2. SCOPE OF ANALYSIS PLAN

This Clinical Pharmacology Analysis Plan (CPAP) defines the end of study noncompartmental analysis (NCA) of pharmacokinetics (PK) of Study 747-302.

Background and Scope

Obeticholic acid (OCA) was approved under the tradename Ocaliva[®] on 27 May 2016 for the treatment of primary biliary cholangitis (PBC) in combination with ursodeoxycholic acid (UDCA) in adults with inadequate response to UDCA, or as monotherapy in adults unable to tolerate UDCA. The indication was approved under the Accelerated Approval regulations based on a reduction in alkaline phosphatase (ALP). Study 747-302 (COBALT) is a postmarketing requirement study conducted to evaluate the effect of OCA on clinical outcomes in subjects with PBC.

Predose/trough plasma samples were collected on Day 1, and at Month 3, 6, 9, and 12; during the follow-up period predose plasma samples were taken annually at 12-month intervals until the end of the study. At Month 9 subjects were given the opportunity to opt into a PK sub study and have plasma samples collected prior to dosing and at 0.5, 0.75, 1, 1.5, 2, 2.5, 3, 4, 5, and 6 hours postdose.

This CPAP describes the evaluation of the data, execution of NCA, and the reporting of pharmacokinetic results. For various reasons, the actual analysis may deviate from the guidance in this document. Deviations from this CPAP will be documented in the clinical study report.

Biomarker (C4, ALP, bile acids, etc.) values will be analyzed as specified in the statistical analysis plan. Further analysis of any PK/ pharmacodynamic (PD) relationships may be explored as the data suggest.

3. STUDY OBJECTIVES

This section presents the study objectives from the protocol to provide context for the scope of this CPAP, as described in Section 2.

3.1. Primary Objectives

To assess the effect of OCA compared to placebo, in conjunction with established local standard of care, on clinical outcomes in subjects with PBC as measured by time to first occurrence of any of adjudicated events as specified in the Study 747-302 final SAP.

3.2. Secondary Objectives

In addition, the SAP specified secondary objectives which includes:

[figure not shown]
- To characterize the pharmacokinetics of OCA and its conjugates in a subset of subjects.

4. STUDY DESIGN

This study started pre-approval as a Phase 3 and continued post-approval as a Phase 4, double-blind, randomized, placebo-controlled, multicenter study to evaluate the effect of OCA on clinical outcomes in subjects with PBC. Subjects were screened twice during a 1 to 8-week Screening period prior to entering the study to allow for the collection of repeat serum chemistry samples (at least 2 weeks apart) to confirm pretreatment ALP and total bilirubin values.

Investigational product was taken orally, once daily for the majority of subjects; dose and frequency were modified for subjects with cirrhosis (including subjects progressing to cirrhosis during the study) and classified as Child-Pugh B or C. The randomization was stratified by ursodeoxycholic acid (UDCA) treatment (yes/ no) and baseline bilirubin categories ($>$ upper limit of normal [ULN]/ \leq ULN).

Figure 1: Study Diagram:

EOS = end of study; ULN = upper limit of normal

Initial dose titration of investigational product should occur at the Month 3 visit, or any study visit thereafter for subjects on all dosing regimens, based on tolerability and biochemical response. Subsequent dose titration(s) for subjects classified as Child-Pugh B or Child-Pugh C and following a modified dosing schedule may occur no earlier than 6 weeks after the previous dose titration.

Dosing frequency was determined by the presence or absence of cirrhosis and, if cirrhosis was present, by CP Score as described below:

- Noncirrhotic subjects or subjects classified as CP-A at screening will receive 5 mg OCA or matching placebo once daily for 3 months. Subjects should titrate to a maximum dose of 10 mg OCA once daily (or matching placebo) at the Month 3 visit or at any study visit following the Month 3 visit based on tolerability and biochemical response of the product.

- For those subjects that up-titrate to 10 mg, dosing may be decreased to 5 mg at any time during the study as considered clinically appropriate (e.g., based on tolerability). Subjects may be titrated back to a maximum dose of 10 mg once daily based on tolerability and clinical judgment of the Investigator.
- Subjects who are cirrhotic and classified as CP-B or CP-C will initiate a modified treatment regimen with 5 mg OCA or matching placebo once weekly for at least 3 months. Subjects classified as CP-B should eventually titrate to a maximum dose of 5 mg OCA or matching placebo once daily, based on tolerability and biochemical response. Subjects classified as CP-C should titrate to a maximum dose and frequency of 10 mg OCA or matching placebo twice weekly, based on tolerability and biochemical response.

Table 1: Planned Dosing Regimen by Cirrhosis and Child-Pugh Score

	Planned Dosing Regimen		
	Standard	Modified	
	Noncirrhotic/ Child-Pugh A	Child-Pugh B	Child-Pugh C
Starting Dose^a (Day 0)	5 mg daily	5 mg once weekly	5 mg once weekly
Titration 1^b (≥Month 3)	10 mg daily	5 mg twice weekly	5 mg twice weekly
Titration 2^b (≥6 weeks after Titration 1)	NA	10 mg twice weekly	10 mg twice weekly
Titration 3^b (≥6 weeks after Titration 2)	NA	5 mg daily	NA

^a Starting dose based on subject's cirrhosis status and Child-Pugh Score at Screening.

^b Planned titration regimen is shown; however, the titration of dose and/or frequency is dependent on subject tolerability, biochemical response, and/or changes in cirrhosis status or Child-Pugh Score at any time during the study

5. SUBJECTS

The study aimed to enroll approximately 428 subjects. At study end, approximately 334 subjects were enrolled, and approximately 40 consented to the serial PK substudy.

6. PK BACKGROUND

Subjects enrolled in the study had trough measurements of OCA and the glyco- and tauro-conjugates determined at 3-month intervals for the first year of the study, and annually thereafter until the end of study. A substudy at 9 months was initiated to determine a plasma concentration/time curve from predose to 6 hours, and to allow imputation of a 24-hour curve.

7. PK SAMPLING

Predose/trough plasma samples were collected on Day 1, and at Month 3, 6, 9, and 12; during the follow-up period predose plasma samples will be taken annually into the follow-up period and at the end of the study.

At Month 9/Week 36 a voluntary PK substudy was conducted at select sites. Subjects had plasma samples collected prior to dosing and at 0.5, 0.75, 1, 1.5, 2, 2.5, 3, 4, 5, and 6 hours postdose. Plasma concentrations of unconjugated OCA, glyco-OCA, and tauro-OCA will be measured using a validated liquid chromatography and tandem mass spectrometry method (LC/MS/MS). Drug concentrations will be reported from the laboratory in units of ng/mL.

In addition, a trough PK sample for the assessment of systemic concentrations of OCA and its major metabolites should be obtained in any patient who develops an adverse event (AE) that is indicative of or consistent with hepatic injury or decompensation.

Subjects in Study 747-302 were randomized to treatment with either OCA or matching placebo in a 1:1 ratio.

8. DATA HANDLING

8.1. Missing Values

The 6-hour PK profile has been optimized for characterization of the early part of the PK profile. A 24-hour profile can be generated by using the predose sample value as the 24-hour timepoint and thus estimating the AUC_{0-24h} . Missing values prior to the first dose will be set to zero; any other missing value will be set to missing and no imputation will be conducted.

8.2. Results Below Limit of Quantification (BLQ)

BLQ values will be imputed to zero for all timepoints prior to the first quantifiable value. BLQ values occurring between 2 quantifiable values will be set to missing. Those BQL values that occur after the last quantifiable value will be set to $\frac{1}{2}$ the lower limit of quantification (LLOQ). Other BLQ approaches may be used with rationale and documentation.

8.3. Results Above Limit of Quantification (ALQ)

Typically, PK and PD samples with concentrations greater than the upper limit of quantification (ULOQ) are diluted into the range of the bioanalytical assay. However, if insufficient sample volume prevents repeat testing of the ALQ sample, the sample will be imputed to the AQL of the assay.

8.4. Handling Anomalous Values

Drug concentration values that appear anomalous may be queried to the bioanalytical laboratory to see if there is a procedural explanation for the incongruous value(s). No repeat testing will be performed on samples for which there is no documented sample collection or bioanalytical error. Handling of anomalous values will be at the discretion of the Clinical Pharmacology Scientist. Final treatment of the anomalous values must be documented in the clinical study report.

8.5. Calculation of Total OCA

Total OCA will be calculated as the molar sum of unconjugated OCA, glyco-OCA, and tauro-OCA, converted back to ng/mL-equivalents of the parent unconjugated OCA.

1. Convert units for each component of total OCA from ng/mL to μM using the molecular weight and formula:

$$\text{Unconjugated OCA } (\mu\text{M}) = \text{unconjugated OCA (ng/mL)} / 420.6 \text{ g/mol}$$

$$\text{Glyco-OCA } (\mu\text{M}) = \text{glyco-OCA (ng/mL)} / 477.7 \text{ g/mol}$$

$$\text{Tauro-OCA } (\mu\text{M}) = \text{tauro-OCA (ng/mL)} / 527.8 \text{ g/mol}$$

2. Sum molar-based components of total OCA:

$$\text{Total OCA } (\mu\text{M}) = \text{unconjugated OCA } (\mu\text{M}) + \text{glyco-OCA } (\mu\text{M}) + \text{tauro-OCA } (\mu\text{M})$$

3. Convert total OCA from μM to ng/mL-equivalents:

$$\text{Total OCA (ng/mL)} = \text{total OCA } (\mu\text{M}) * 420.6 \text{ g/mol}$$

Note that if there is not a valid value (BLQ imputations are valid) for one or more of the components of total OCA (unconjugated OCA, glyco-OCA, or tauro-OCA) then total OCA will not be calculated.

8.6. Number Precision

Drug concentration values from the bioanalytical laboratory will not be rounded prior to use in NCA. Total OCA $\text{AUC}_{0-6\text{h}}$ and $\text{AUC}_{0-24\text{h}}$ values will be reported in the outputs from WinNonlin (Section 11) to the default precision dictated by the WinNonlin software.

8.7. Actual versus Nominal Times

Actual collection times will be used for NCA. In cases where nominal times are used, a rationale will be documented.

9. SOFTWARE USED

NCA-ready datasets may be produced using SAS Version 9.4 or higher. NCA will be performed using Phoenix WinNonlin Version 8 or higher.

10. SUBJECT POPULATION TO BE ANALYZED

The process described herein will be executed for the PK populations as described in the protocol.

- The PK population will include all OCA subjects who have at least one confirmed fasted analyzable sample. Subjects must have been fasting for approximately 8 hours prior to the visit and must not have any major protocol deviations that potentially affect exposure levels. The PK population will be used for OCA PK analyses.

11. PROCESS FOR ANALYSES

The end of study NCA for Study 747-302 will follow the steps described below.

- An analysis-ready dataset is created by merging the dosing and PK sampling data with the drug concentration data for unconjugated OCA, glyco-OCA, tauro-OCA, and total OCA
 - Units for concentrations will be ng/mL and units for time will be hours
 - Actual time since last dose will be calculated as the time variable. While PK parameters will be calculated for PK profiles with deviations from nominal times, gross deviations may render PK parameters incompatible for inclusion in summary statistics. In such a case, the parameters in question would be included in listings (and flagged) but excluded from summary tables and figures.
 - BLQ values will be imputed as per [Section 8.2](#).
 - Total OCA will be calculated as per [Section 8.5](#). In general, Categorical variables will be summarized by counts and by percentage of subjects in corresponding categories.

Evaluation of the data should include:

- The drug concentrations and PK parameters will be available for:
 - Unconjugated OCA
 - Glyco-OCA
 - Tauro-OCA
 - Total OCA (molar sum of OCA, glyco-OCA, tauro-OCA)
- Examples of potential reasons for exclusion of data from PK summary analyses include, but are not limited to:
 - Subject not fasted for 8 hours prior to PK visit
 - Subjects not adhering to standardized meal timing (or missed meal) during PK profile collection
 - Non-standard dosing (e.g., drug holiday, altered dose level, altered dose frequency) used prior to PK visit

Data excluded based on this review will be included in listing outputs (and flagged with footnote) but will be excluded from summary tables and figures.

- Drug concentration data in ng/mL units will be summarized by analyte (unconjugated OCA, glyco-OCA, tauro-OCA, and total OCA), baseline CP category (or noncirrhotic), dosing regimen, study visit, and timepoint using the following descriptive statistics: n, number and % BLQ, arithmetic mean, SD, CV%, minimum, median, maximum, interquartile range, geometric mean, and geometric CV%.
- Trough PK samples for the assessment of plasma concentrations of OCA and its conjugates, obtained in any subject who develops an AE that is indicative of or

consistent with hepatic injury or decompensation, will be summarized separately from scheduled PK collections and stratified by baseline CP category (or noncirrhotic) and dosing regimen.

- Actual collection date and time, time since reference dose, time deviation between actual and nominal collection times, flags for exclusion from summaries, and stratification variables should be included.
- PK concentration summary tables presenting descriptive statistics over time by analyte and including stratification by any relevant factors.

PK parameters will be calculated and examined using the execution of NCA ([Section 11.2](#)). The data will be summarized as follows:

- PK parameters will be calculated in subjects at Month 9 for whom a PK profile can be produced. Parameters to be calculated are found in [Table 2](#).
- Individual PK parameters for unconjugated OCA, glyco-OCA, tauro-OCA, and total OCA will be listed by subject and include information for baseline CP category, dosing regimen, study visit, and timepoint.
- PK parameters will be summarized by analyte (unconjugated OCA, glyco-OCA, tauro-OCA, or total OCA, PK parameter, baseline CP Category (noncirrhotic, CP-A, CP-B, or CP-C), baseline MELD category ($>/\leq 8$ and $>/\leq 11$), dosing regimen (dose strength/frequency), and study visit. For the “All Visits” category, if an individual subject has data from multiple visits on a particular dosing regimen, the mean of the values across those visits will be used so that each subject is only represented once. The summary statistics to be used for each PK parameter are described in [Table 3](#). Reporting precision is generally to 3 significant figures except for the following: time to achieve peak (maximum) plasma concentration (T_{max}) is reported to same precision as nominal time, SD is reported to same precision as mean and median, and CV and geometric CV are reported to the same precision as mean and geometric mean, respectively.
- The following figures will be produced for mean concentration data for all analytes:
 - Mean (+SD) 6-hour and 24-hour PK profiles for unconjugated OCA, glyco-OCA, tauro-OCA, and total OCA will be provided as follows:
 - Nominal hours on continuous x-axis
 - Mean (+SD) plasma concentration (ng/mL) on linear y-axis
 - Unconjugated OCA, glyco-OCA, tauro-OCA, and total OCA are presented on same figure (5 lines)
 - Outputs should present one visit per page which will involve a matrixed panel of figures to stratify for CP category (or noncirrhotic) and dosing/regimen at each visit.
- Boxplots of the relevant AUCs (AUC_{0-6h} and AUC_{0-24h}) will be provided for each PK study visit, stratified by baseline CP category (or noncirrhotic) and the dosing regimen used at the time of the PK visit. Separate figures will be produced for

- unconjugated OCA, glyco-OCA, tauro-OCA, and total OCA. Boxplots will also include the individual AUC values from each subject.
- Boxplots of C_{trough} will also be generated. Separate figures will be generated for unconjugated OCA, glyco-OCA, tauro-OCA, and total OCA at each PK study visit (Day 0, Month 3, Month 6, Month 9, Month 12, and annual visits thereafter). Stratification within each figure will be by CP category (noncirrhotic and CP-A subjects only) and the dosing regimen used at the time of the PK visit. Boxplots will also include the individual C_{trough} values from each subject.
 - Statistical comparisons (e.g., Proc Mixed) of the ln-transformed PK parameters from Study 747-302 will compare exposures from the following groups: noncirrhotic 5 mg OCA daily, CP-A 5 mg OCA daily, noncirrhotic 10 mg OCA daily, and CP-A 10 mg OCA daily. Separate analyses will be performed for each PK parameter/Visit to include total OCA AUC_{0-6h} from Month 9 and total OCA C_{trough} from Month 3, Month 6, Month 12, or subsequent annual visits (provided sufficient data are available). The geometric least-squares (LS) means, geometric LS mean ratios (test/reference), and associated 90CIs will be presented and will be exponentiated to the original scale. The reference group presented will alternately be the 5 mg OCA daily noncirrhotic group or the 10 mg OCA daily noncirrhotic group. Additional analyses may be generated if deemed appropriate.
 - PK parameter summaries may be re-analyzed as a function of the key subgroups following the preliminary PK analysis.
 - Depending on the information available for biomarkers, PK/PD analyses may be performed if deemed appropriate. The description of these analyses will be provided on an ad hoc basis.

In addition, trough PK samples for assessment of drug concentrations of OCA and its conjugates, obtained in any patient who develops an AE that is indicative of or consistent with hepatic injury or decompensation, will be identified as such in the listings. The actual and nominal sampling times of PK sample collection will also be listed for each subject and will include the deviation in time from nominal, if applicable. All measured concentrations will be presented in original units as reported by the bioanalytical lab (i.e., ng/mL). Columns in the listing for unconjugated OCA, glyco-OCA, tauro-OCA, and total OCA will be displayed on the same page. Any individual concentrations excluded from summaries or analyses will be flagged and footnoted.

If the values for one or more of the components of total OCA are missing, then total OCA will not be calculated and will be set to missing. If the value for one or more of the components of total OCA are BLQ then appropriate BLQ imputation will be performed prior to the calculation of total OCA. Total OCA will be calculated in units of “unconjugated OCA ng/mL equivalents” but for the sake of brevity, total OCA results will be reported in units of “ng/mL.”

Table 2: PK Parameters to be Calculated for Study 747-302

PK Parameter	Units	Definition
AUC _{0-6h}	ng*h/mL	Area under the concentration versus time curve from zero time to 6 hours. The linear/linear trapezoidal rule should be used for estimation of AUC. At least 4 quantifiable concentration-time values must be available to compute AUC _{0-6h}
AUC _{0-24h}	ng*h/mL	Area under the concentration versus time curve from zero time to 24 hours. The predose sample for each profile is to be used as the 24-hour timepoint. The linear/linear trapezoidal rule should be used for estimation of AUC. At least 4 quantifiable concentration-time values must be available to compute AUC _{0-24h}
C _{max}	ng/mL	Maximum observed concentration. If all observations are BLQ, C _{max} will be reported as zero
C _{trough}	ng/mL	Pre-dose concentration
T _{max}	H	First time at which C _{max} is observed. If all observations are BLQ, T _{max} will be reported as not determined (ND)
MR _{AUC}	unitless (ratio)	Molar metabolite to parent ratio for AUC _{0-6h}
MR _{Cmax}	unitless (ratio)	Molar metabolite to parent ratio for C _{max}

Table 3: PK Parameter Summary Statistics

Variable	Summarized with:
AUC _{0-6h} , AUC _{0-24h} , C _{trough} , C _{max} , MR _{AUC} , and MR _{Cmax}	n, arithmetic mean, SD, CV%, minimum, Q1 (25% percentile), median, Q3 (75% percentile), maximum, geometric mean and geometric CV%
T _{max}	n, minimum, Q1 (25% percentile), median, Q3 (75% percentile) and maximum

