11.2. Execution of NCA

Using the analysis-ready dataset, NCA will be performed according to the following:

- Review data on fed status prior to dosing and prior to 24-hour sampling
- Review data on dose (mg) and timing of meal during PK profile
- Exploratory data analysis will be performed by creating XY plots of concentration versus actual time, grouped by analyte (unconjugated OCA, glyco-OCA, tauro-OCA, and total OCA) to inspect the PK profiles
- NCA will be performed for each analyte with the following settings:
 - Linear trapezoidal/linear interpolation methodology
 - ‘Disable Curve Stripping’ setting to avoid calculation of an elimination slope
 - Use of actual time since last dose as time variable (hours)
- Calculate the AUC_{0-6} . Estimate AUC_{0-24h} by using the predose value and setting that value to 24 hours.
- Carry the study, subject, and visit variables into the analysis for output purposes

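### AUC0-24h takes the predose sample as its 24-hour value for every regimen, so it reads low for subjects on weekly or twice-weekly dosing at the PK visit

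*SAP*

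**What the plan says.** The rule stands in three places of the CPAP, each time without a condition on regimen.

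- Section 8.1 (Missing Values): "A 24-hour profile can be generated by using the predose sample value as the 24-hour timepoint".
- Section 11, Table 2, definition of AUC0-24h: "The predose sample for each profile is to be used as the 24-hour timepoint".
- Section 11.2 (Execution of NCA): AUC0-24h is estimated "by using the predose value and setting that value to 24 hours".

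The substitution is needed because the Month 9 profile stops at 6 hours. Section 7 says: "Subjects had plasma samples collected prior to dosing and at 0.5, 0.75, 1, 1.5, 2, 2.5, 3, 4, 5, and 6 hours postdose". For the area, Table 2 adds: "The linear/linear trapezoidal rule should be used for estimation of AUC".

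Not every subject is dosed daily. CPAP Section 4 says that cirrhotic subjects in Child-Pugh class B or C "will initiate a modified treatment regimen with 5 mg OCA or matching placebo once weekly for at least 3 months", and its Table 1 then moves them to twice weekly. The dosing table in main SAP Section 3 requires twice-weekly doses to be at least 3 days apart.

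AUC0-24h is reported for these subjects. CPAP Section 11 summarises PK parameters by baseline Child-Pugh category, including B and C, and by regimen. It also draws AUC boxplots "stratified by baseline CP category (or noncirrhotic) and the dosing regimen used at the time of the PK visit" and panels the mean 24-hour profiles by the same factors. Section 12.1 lists daily versus modified dosing among the key subgroups.

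**The concern.** A predose concentration equals the 24-hour concentration only when doses are 24 hours apart and the subject is at steady state. With gaps of several days, the predose sample is the tail of a much longer interval and lies below the concentration 24 hours after the dose. Copying it to hour 24 pulls down the whole 6 to 24 hour part of the curve, which is 18 of the 24 hours.

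The affected subjects are hepatically impaired subjects on modified dosing, and the error makes their exposure look lower than a real 24-hour sample would. Because AUC0-24h is laid out by regimen, a reader would be comparing a sound daily value with one that is systematically low.

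**Working it through.** The documents give no AUC, half-life or 24-hour concentration, so there is no plan figure to reproduce. The direction follows from the CPAP's own rules. The size needs assumptions.

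**Inputs from the documents**
- Last postdose sample at 6 h (CPAP Section 7).
- Linear trapezoid (CPAP Table 2).
- C24 set to Cpredose (CPAP Sections 8.1 and 11.2, Table 2).
- Dosing gaps: 24 h (daily); 72 and 96 h (twice weekly, at least 3 days apart); 168 h (weekly).

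**Step 1: direction.** The 0–6 h area is the same either way. The 6–24 h area is:

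- with a real 24-hour value: 18 × (C6 + C24)/2 = 9 × (C6 + C24)
- under the rule: 9 × (C6 + Cpredose)

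Rule minus real = 9 h × (Cpredose − C24). For daily dosing at steady state, Cpredose = C24 and the difference is zero. For gaps of 72 to 168 h, with concentrations falling between hour 24 and the next dose, Cpredose < C24 and the difference is negative.

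**Step 2: size, under assumptions not in the documents.** One-compartment model with first-order absorption at steady state, absorption rate 0.5 or 1.0 per hour, half-life 4 to 96 h, and the CPAP's sampling times. The table gives the change in the whole AUC0-24h against the same trapezoid with a real 24-hour value. Ranges span both absorption rates and, for twice weekly, both gaps.

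| Half-life (h) | Cpredose/C24 at 72 / 96 / 168 h | Daily | Twice weekly | Weekly |
|---|---|---|---|---|
| 4 | 0.000 / 0.000 / 0.000 | 0% | −2.3 to −3.0% | −2.3 to −3.0% |
| 8 | 0.016 / 0.002 / 0.000 | 0% | −10.9 to −12.8% | −11.1 to −12.8% |
| 12 | 0.062 / 0.016 / 0.000 | 0% | −16.7 to −19.5% | −17.8 to −19.9% |
| 24 | 0.236 / 0.132 / 0.016 | 0% | −20.6 to −25.4% | −26.8 to −29.1% |
| 48 | 0.462 / 0.383 / 0.125 | 0% | −17.4 to −21.1% | −28.7 to −30.6% |
| 96 | 0.665 / 0.632 / 0.354 | 0% | −11.7 to −13.3% | −22.9 to −24.0% |

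The shortfall is small at a 4 h half-life because C24 is itself small. For twice-weekly dosing it shrinks again at long half-lives because the predose value is then no longer far below C24.

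**Step 3: who is affected.** CPAP Table 1 gives Child-Pugh B subjects a third titration step, to daily dosing. Two further steps of at least 6 weeks after Month 3 put this at about day 90 + 42 + 42 = 174 at the earliest, before the Month 9 target of day 274 in the main SAP visit windows. A Child-Pugh B subject may therefore be on daily dosing at the profile, where the rule is sound. The dosing table in main SAP Section 3 shows no daily step for class B. For class C, neither table has a daily step.

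**The case against.** The strongest reply is that little depends on AUC0-24h. The formal comparisons in CPAP Section 11 cover noncirrhotic and Child-Pugh A subjects on daily dosing, and name AUC0-6h and Ctrough. The AUC metabolite ratio in Table 2 uses AUC0-6h. The AUC0-24h displays are stratified by regimen, so modified-regimen values are not silently pooled with daily ones. Section 12.1 makes further subgroup assessment optional and lets cells below 5 be skipped. Sections 6 and 11.2 present the 24-hour curve as imputed and its AUC as an estimate. All of this stands and confines the point to descriptive outputs. It does not make the rule valid where it is applied.

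Two provisions might seem to rescue the rule. Section 11 gives altered dose frequency as an example of a reason for exclusion, but as non-standard dosing, and the planned modified regimens are not clearly that. Section 11.2 mentions reviewing fed status before 24-hour sampling, but the Section 7 schedule contains no 24-hour sample.

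A reader might infer more than the documents support, in four ways.

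- **Larger errors.** With a predose value of zero, the 6–24 h area is short by 20%, 33% or 43% when C24/C6 is 0.25, 0.50 or 0.75. These figures cover that segment only, not AUC0-24h. The last also contradicts itself. With mono-exponential decline, a ratio of 0.75 over 18 h means k = ln(1/0.75)/18 = 0.016 per hour, a half-life of about 43 h. Predose is then 0.35, 0.24 or 0.075 of C6 at 72, 96 or 168 h, and the segment shortfall is 23%, 29% or 39%.
- **Understatement of true exposure in every case.** In the same model at a 4 h half-life, the linear trapezoid overshoots the true integral in all regimens: about +28% for daily, +24% to +26% for the others. Modified regimens still read low relative to daily.
- **All Child-Pugh B and C subjects.** Under CPAP Table 1, some class B subjects may be on daily dosing by Month 9.
- **A known number affected.** CPAP Section 5 gives only about 40 consenting to serial sampling, in a 1:1 randomised trial. The number on modified dosing is not stated.

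**Conclusion.** The rule is wrong as written for subjects on weekly or twice-weekly dosing at the PK visit. Their AUC0-24h is too low by 9 h × (C24 − Cpredose) against the same trapezoid with a real 24-hour value, so it is not comparable with daily regimens. The direction rests on the CPAP's own intervals and area rule, and on concentrations falling between hour 24 and the next dose. The size, about 2–25% (twice weekly) and 2–31% (weekly), rests wholly on the assumed half-lives of 4 to 96 h and the one-compartment model.

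The harm is limited to descriptive AUC0-24h summaries, boxplots, 24-hour profile figures and any daily-versus-modified subgroup assessment that uses AUC0-24h. The formal PK comparisons, the metabolite ratios and the trial's efficacy analyses are untouched.

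**What to change.** In CPAP Section 8.1, Table 2 and Section 11.2, limit the predose-for-24-hour substitution to subjects on once-daily dosing at the PK visit. Apply the same limit to AUC0-24h and to the 24-hour profile figures in Section 11. For weekly and twice-weekly regimens, report AUC0-6h, Cmax and Ctrough, with a footnote saying why AUC0-24h is not given. Define the restriction by regimen at the visit, not by Child-Pugh class.

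The cost is about one sentence in each place. AUC0-24h is lost only for subjects in whom the substitution does not hold, and no collected data are discarded.

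Separately, the dosing table in main SAP Section 3 and CPAP Section 4 with its Table 1 disagree on whether Child-Pugh B subjects reach daily dosing. They must be reconciled, because this settles which planned regimens fall under the restriction.
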